Caregivers of adults with dementia report significant stress and poor self-care. Virtual Caregiver Coach for You (ViCCY ["Vicky"]), a virtual support intervention, may relieve stress and promote self-care in dementia caregivers. Even less is known about the effect of caregiver support interventions on dementia patient outcomes. Thus, we propose to extend the novel self-care support intervention ViCCY ("Vicky") to caregivers of persons with behavioral variant frontotemporal dementia (bvFTD) and we will explore the effect of caregiver outcomes on bvFTD patient outcomes. This work will allow us to develop a new and innovative way to increase support that is urgently needed to reduce poor outcomes in this distressed and underserved caregiver population.

OBJECTIVES:

Aim 1: Compare the preliminary efficacy of ViCCY vs. Health Information (HI) alone in improving self-care in FTD caregivers. We hypothesize that, at 6 months after enrollment, caregivers randomized to ViCCY vs. HI alone will have H1a: Improved self-care measured with the Self-Care Inventory (primary outcome); H1b: Reduced self-reported stress measured with the Perceived Stress Scale (secondary outcome); H1c: Reduced depression measured with Center for Epidemiologic Studies Depression Scale (CES-D; secondary outcome); H1d: Improved coping measured with the Ways of Coping Questionnaire, short form (secondary outcome); H1e: Reduced burden measured with Zarit Burden Interview (ZBI; secondary outcome); and H1f: improved perceived mental and physical health status measured with the SF-36 (secondary outcome).

Aim 2: Explore the effect of caregiver outcomes on FTD patient outcomes. We hypothesize that, at 6 months after enrollment, FTD patients whose caregivers improve vs. not improve in self-care – regardless of group – will demonstrate H2a: Fewer behavioral symptoms measured with the Frontotemporal Dementia Rating Scale (primary outcome) and Neuropsychiatric Inventory (secondary outcome).

BACKGROUND:

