Evaluation of perceived efficacy of the intervention at 1 month will be evaluated with the Credibility-Expectancy scale to measure intervention credibility and treatment expectancy early on in the study. The Credibility-Expectancy scale is reliable ($\alpha=0.84$) and consists of 6 items scored on a 9 point Likert scale.

Caregiving characteristics will be collected at baseline in a sociodemographic survey interview format to assess work performance with the 7-day work performance questionnaire. This measure has 13 items of 10-pt scale, dichotomous assessment, and a record of number hours spent performing paid and unpaid work; $\alpha = 0.73$.

The Protocol for Responding to and Assessing Patients Risk and Experiences (PRAPARE) is a tool kit developed by the National Coalition on Community Health Centers to standardize the collection of data on social determinants of health (SDH) and facilitate its integration into health records, as a response to recommendations from the National Academy of Medicine. The PRAPARE has 16 core domains (Race, Ethnicity, Education, Employment, Insurance, Income, Material Security, Transportation, Stress, Housing stability, Housing status, Language, Veteran status, Address/Neighborhood, Migrant/seasonal farm work and Social integration/support) and four optional domains (Incarceration history, Safety, Refugee status and Domestic Violence) that align with Healthy People 2020 and the Center for Disease Control and Preventions agenda for prioritizing SDH in health centers.

Patient characteristics and outcomes will be assessed at baseline with the modified Clinical Dementia Rating Scale (mCDR) which includes behavior and language domains. We will also use the Frontotemporal Dementia Functional Rating Scale (FTD-FRS) and the Neuropsychiatric Inventory (NPI) to measure behavioral and psychological symptoms of dementia

2. Group Modifications:

No modifications have been made for the study instruments described above.

3. Method for Assigning Subjects to Groups:

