Assessments of self-care, perceived stress, depression, burden, coping, relationship quality, and health status will be conducted at baseline (after enrollment but prior to randomization) and by phone at 3 and 6 months. We will also collect the credibility-expectancy scale at 1 month to evaluate treatment expectancy. Using contrasts within a mixed-effect modeling framework, we will assess intervention efficacy at 6 months using intention-to-treat analysis. We provide 10 health coaching sessions based on pilot data and literature demonstrating that a shorter duration of health coaching is not routinely effective. We chose to assess the primary aim at 6 months based on prior psychosocial intervention studies, but we will also assess outcomes at 3-months based on this rationale: baseline (enrollment), to generate consistent profiles of all enrollees at a consistent point in time and prior to implementation of the intervention; at 3-months to evaluate very early effects; and at 6-months to demonstrate efficacy of the intervention. Our goal is to establish preliminary efficacy and in a future study we will evaluate longer terms effects of ViCCY vs. HI at 6-months.

If a subject can no longer participate in the study safely or due to changes in circumstance that prevents participation (e.g., imprisonment, long term hospitalization, etc.) they will be withdrawn from the study. Data collection will not continue for participants who are withdrawn from the study. If applicable, research staff will arrange to collect study equipment from the participants who are withdrawing.

STUDY PROCEDURES:

1. Detailed Description:

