We will use a RCT design to achieve robust and unbiased results, as detailed below. We will enroll 30 informal bvFTD caregivers and the bvFTD patients for whom they care. After collecting baseline data, we will block randomize the caregivers 1:1 to the intervention or control group, stratifying randomization by caregiver sex and relationship to the patient (e.g., spouse, adult child) factors known to influence caregiving burden, perceived stress, and receptivity to the intervention. We will provide tablet devices with wireless network access and connect caregivers in both conditions to the Internet so they can access the Internet site providing Health Information (HI) content, which will be the only content provided to caregivers in the control group. In addition to HI, the intervention group will receive 10 front-loaded sessions of ViCCY over 6 months. To safeguard confidentiality, tablets provided to caregivers can only be used for the study. Assessments of self-care, perceived

stress, coping, and health status will be conducted at baseline (after enrollment but prior to randomization) and by phone at 3 and 6 months. Using contrasts within a mixed-effect modeling framework, we will assess intervention efficacy at 6 months using intention-to-treat analysis. We chose to provide 10 health coaching sessions based on our pilot data and literature demonstrating that a shorter duration of health coaching is not routinely effective. We chose to assess the primary aim at 6 months based on prior psychosocial intervention studies, but we will assess outcomes at 3-months based on this rationale: baseline (enrollment), to generate consistent profiles of all enrollees at a consistent point in time and prior to implementation of the new intervention; at 3-months, very early effects, at 6-months longer-term effects of ViCCY. We will pull resource use data from the electronic medical record (EMR) in 30-day increments and validated these data during routine follow-up calls with caregivers. We expect the proposed study to require 5 years for completion.

2. Data Collection:

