To assess changes in each of the primary and secondary outcomes over time, separate mixed effects regression models will be generated with SAS Proc Mixed. We are not powered for secondary outcomes (e.g., stress, coping, health status), but we will examine effect sizes and confidence intervals (CIs) to determine if lack of power is driving nonsignificant results. Mixed models can account for correlation between repeated measures and handle non-excessive MAR or MCAR data better than traditional models and allow for use of time-independent and time-dependent covariates. Both random slopes and random intercepts will be modeled to represent deviations from the average, or fixed-effect, slope over time and intercept, respectively. REML will be used for parameter estimation and the most appropriate covariance structure will be examined. Scores will be analyzed as repeated observations, with mean-centered baseline outcome scores serving as a covariate. Other predictor variables will include group, assessment time, and the interaction of group time (primary effect of interest). Baseline measures and group will be analyzed as time-independent covariates. The evaluation of differences in outcome profiles over time according to group will rely on the group x time interaction terms, while differences by the balancing

variables will rely on the mixed-effects modeling of higher order interaction terms. Statistical significance for individual intervention contrasts will be evaluated for each outcome, applying the Benjamini & Hochberg method to control for the type I error rate at 5%. The Akaike information criterion (AIC) will be used to evaluate overall model fit and to select the best-fitting longitudinal change pattern. We expect the groups to be balanced on baseline characteristics due to randomization; however, imbalances that occur by chance will be adjusted for in all analyses. To evaluate patient outcomes (Aim 2) over time we will use mixed effects regression modeling. As described above, scores will be analyzed as repeated observations, with mean-centered baseline outcome scores serving as a covariate. Other predictor variables will include time-dependent caregiver variables, assessment time, and the corresponding two-way interaction term (primary effect of interest).

RISK/BENEFIT ASSESSMENT:

1. Risks:

Protection Against Risk:

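### The effect named as primary for Aim 2 (caregiver variable by time) is not, on the most literal reading, the 6-month difference that H2a states, and can miss it when it is real

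*Combined protocol and SAP*

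**What the plan says.** **Hypothesis (OBJECTIVES, Aim 2).** H2a is set "at 6 months after enrollment, FTD patients whose caregivers improve vs. not improve in self-care", in either arm. The predicted result is "Fewer behavioral symptoms measured with the Frontotemporal Dementia Rating Scale (primary outcome) and Neuropsychiatric Inventory (secondary outcome").

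**Analysis (STUDY PROCEDURES, 5. Statistical Analysis).** Aim 2 uses a mixed model: "As described above, scores will be analyzed as repeated observations, with mean-centered baseline outcome scores serving as a covariate". The next sentence names the effect of interest: "Other predictor variables will include time-dependent caregiver variables, assessment time, and the corresponding two-way interaction term (primary effect of interest"). Earlier in the section, for the outcome models generally: "Both random slopes and random intercepts will be modeled to represent deviations from the average".

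**Measurement.** METHODS, 1. Study Instruments says "We will also use the Frontotemporal Dementia Functional Rating Scale (FTD-FRS) and the Neuropsychiatric Inventory (NPI) to measure behavioral and psychological symptoms of dementia", without a visit or a respondent. The list in METHODS, 6. Subject Follow-up begins "Assessments of self-care, perceived stress, depression, burden, coping, relationship quality, and health status will be conducted at baseline (after enrollment but prior to randomization") and continues with phone calls at 3 and 6 months. It names neither patient scale. STUDY PROCEDURES, 1. Detailed Description has a shorter list (self-care plus "stress, coping, and health status will be conducted at baseline (after enrollment but prior to randomization) and by phone at 3 and 6 months"), also without them.

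No section defines 'improve', names self-care as the caregiver variable in the Aim 2 model, or sets a 6-month contrast for Aim 2. The 6-month contrast in Subject Follow-up and in Detailed Description is for intervention efficacy.

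**The concern.** The hypothesis is about a level at one visit; the named test is about a change between visits. If an analyst follows the Statistical Analysis section literally, a steady benefit to patients of improving caregivers would probably be reported as a null primary result for Aim 2, even with a clear 6-month difference in the data. Because neither the caregiver variable nor 'improve' is fixed, the choice among several caregiver scales and several codings also stays open until data are seen. Aim 2 is exploratory, but it has its own hypothesis and a designated primary outcome, and STUDY DESIGN gives it as the reason for enrolling patients.

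**Working it through.** **No figure in the plan to reproduce.** The only power statement (over 90% with 15 caregivers per arm) concerns the Self-Care Inventory in Aim 1. Its inputs are not given, and nothing below depends on it.

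**Step 1: algebra, no assumed inputs.** Let D3 and D6 be the improver minus non-improver differences in patient score at months 3 and 6, adjusted for baseline score. With baseline as a covariate and two follow-up responses,

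interaction = D6 − D3, whereas H2a concerns D6.

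- D3 = D6 = D: interaction = D − D = 0, whatever D and the sample size.
- D3 = D/2, D6 = D: interaction = D/2, half of what H2a concerns.
- D3 = 0, D6 = D: interaction = D.
- D3 = D, D6 = 0: interaction = −D. H2a is false and the sign is opposite to a benefit.

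**Step 2: size, with a fixed improver indicator.** From the documents: 30 dyads, visits at 3 and 6 months, 5% level. Assumed: two-sided test, 15 improvers and 15 non-improvers, unit SD, common correlation r of 0.5 to 0.7 between visits, no dropout. Then

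- SE(interaction) = √[2(1 − r)] × √(2/15) = 0.365 (r = 0.5) or 0.283 (r = 0.7)
- SE(month 6) = √(1 − r²) × √(2/15) = 0.316 (r = 0.5) or 0.261 (r = 0.7)

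A 1 SD difference is therefore 2.74 or 3.54 standard errors for the interaction, when it is present at one visit only, and 3.16 or 3.83 for the month-6 contrast. Simulated rejection rates (10,000 trials per cell, benefit coded negative):

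| D3, D6 (SD) | Interaction | Month-6 contrast |
|---|---|---|
| −1, −1 | 5% | 85–95% |
| −0.5, −1 | 26–39% | 85–95% |
| 0, −1 | 74–91% | 85–95% |
| −1, 0 | 74–92% (mean estimate +1.00) | 5% |

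**Step 3: size, with a time-dependent caregiver variable.** Assumed: the variable is change in the Self-Care Inventory (SCI) to the same visit, correlated 0.7 between visits; residual correlation 0.6; baseline-score coefficient 0.6; partial correlation of SCI change with patient score 0.4 / 0.5 / 0.6; 30 dyads, no dropout, 4,000 trials per cell, compound-symmetric covariance. The month-6 tests use SCI change from baseline to 6 months. The median-split column is adjusted for baseline patient score, baseline SCI and arm.

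| Association | Interaction | Month 6, median split |
|---|---|---|
| Equal at both visits | 4.4 / 5.2 / 5.2% | 37.3 / 57.0 / 74.6% |
| Half as large at month 3 | 21.8 / 34.5 / 51.3% | 36.6 / 54.3 / 75.6% |
| Absent at month 3 | 63.9 / 85.4 / 96.4% | 37.3 / 57.1 / 75.6% |
| Month 3 only | 64.0 / 86.3 / 96.5% | 5.0 / 5.0 / 4.5% |

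Across the first three patterns, the month-6 test on continuous SCI change rejects in 55.8–57.0 / 76.6–78.8 / 92.7–93.5%. With adjustment for baseline patient score only, the median-split test in the equal pattern rejects in 39–79%. In the last pattern, 0% of trials gave a significant interaction in the direction that supports H2a.

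**Step 4: does another reading fit?** A random intercept, a random slope, their covariance and a residual variance make 4 parameters. Two follow-up visits supply 2 variances + 1 covariance = 3. The random-effects sentence therefore fits better if baseline is also a response (3 variances + 3 covariances = 6). With baseline as a response and a fixed 0–6 month SCI change crossed with linear time, the interaction rejects in 54.3–55.2 / 76.8–78.8 / 92.5–93.4% across the first three patterns, close to the continuous month-6 test. With the same fixed change but baseline kept as a covariate, it rejects in only 10.1 / 15.5 / 20.7% in the equal pattern.

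**The case against.** The best defence is that the section is ambiguous. Random slopes over time make little sense with two follow-up responses, so the authors may have meant baseline, 3 and 6 months all to be responses. With a fixed 0–6 month caregiver change, the interaction would roughly test H2a. This stands as a reason for moderate confidence. It does not remove the point, because the text calls the baseline score a covariate and the caregiver variables time-dependent.

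Second, the loss depends on the pattern. It is near-total only when the association is equal at both visits. If it appears only at month 6, the interaction in Step 3 is ahead of the median split (64–96% against 37–76%) and slightly ahead of continuous SCI change. In Step 2, with a fixed indicator, the month-6 contrast stays ahead. The fitted model also contains the caregiver main effect, so a steady association would still be estimated, though not as the primary effect.

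Third, the missing pieces can partly be inferred. H2a names self-care, and H1a measures it with the Self-Care Inventory. That helps, but it does not say what counts as improvement.

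A reader might infer that the interaction can produce false support for H2a. It cannot in the case that suggests this: the month-3-only results, though often significant, point the other way and show a fading association. A reader might also infer that FTD-FRS and NPI will not be collected after baseline. The documents do not say so: H2a's time point and the repeated-observations wording imply follow-up scores, and the lists are not exhaustive (the one in Detailed Description also leaves out depression and burden).

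**Conclusion.** The point holds on the most literal reading, with medium confidence. The primary effect named for Aim 2 estimates D6 − D3, not the month-6 difference in H2a. It has no power beyond the test level when a true benefit is equal at both visits, and it loses power when the benefit is partly present at month 3 (22–51% against 37–76% in Step 3).

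The algebra needs only the two-response reading. Every percentage rests on assumed correlations, effect sizes and no dropout, since the documents give none of these for Aim 2. The missing visit times for FTD-FRS and NPI are an accompanying omission to reconcile.

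The consequence is confined to an exploratory aim. The Aim 1 comparison is untouched, and no power is claimed for Aim 2. It is worth fixing because, as written, a null primary result for Aim 2 could not be read as evidence against H2a.

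**What to change.** 1. In STUDY PROCEDURES, 5. Statistical Analysis, make the Aim 2 primary effect the month-6 contrast from the mixed model, with visit as a category and baseline patient score as covariate, for caregiver improvement on the Self-Care Inventory from baseline to 6 months. Report it with its 95% CI. Keep the interaction with time as secondary.
2. Fix the definition of 'improve' before database lock. Also report the effect of continuous SCI change at 6 months, which usually has more power (56–94% against 37–76% under the Step 3 inputs). Further adjustment for baseline SCI and arm is optional.
3. State that improver status is not randomized, so the result is an association.
4. Add FTD-FRS and NPI to Study Instruments, Subject Follow-up and Detailed Description at baseline and 6 months, and at 3 months if the repeated-measures model is kept. Name the respondent, and check this against Subject Recruitment and Screening, which describes patient consent for record review and the modified Clinical Dementia Rating only.

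**Cost.** Wording changes, with no extra participants or visits. Assessments may be longer, depending on who responds, and the consent wording may need a change. Power may be lower than the interaction's if the association emerges only at month 6.

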Effective interventions are needed for FTD caregivers. Given the challenges outlined above, there is an urgent need to develop supportive interventions for FTD caregivers that are flexible in nature. A recent scoping review found only five intervention studies targeting FTD caregiver stress, but these were mainly limited to small pilot studies exploring the use of support groups. While support groups are an important resource for FTD caregivers, geographical barriers as well as caregiving and life demands severely limit attendance. Web-based interventions may be an effective solution to overcome these accessibility barriers as the home environment may be the best place to deliver an intervention, where distractions are predictable and privacy can be optimized. Home interventions are perceived as convenient, requiring less time commitment, travel costs, financial costs, and waiting times; duration and timing of sessions can be flexible and accommodate caregiver preferences. Indeed, web-based interventions for dementia caregivers have been reported to be convenient and beneficial in reducing caregiver depression and stress, yet these studies have been limited to forms of dementia like Alzheimer's disease

where the caregiving experience significantly differs from that of FTD. Therefore, we propose to extend the intervention, ViCCY, to address these gaps by offering: 1) a psychosocial rather than purely educational approach; 2) flexibility; 3) multidimensionality including information and support tailored for the specific needs of FTD caregivers.

Dyadic processes influence patient behavioral symptoms. Caring for a person with bvFTD is extremely challenging. Caregivers often misinterpret patient behavioral symptoms such as apathy or disinhibition as a sign of volitional opposition and poor cooperation, leading to high level of stress and dissatisfaction with caregiving. Studies have demonstrated that caregivers must adjust their own affect and demeanor to meet the needs of the patient with behavioral symptoms and negative emotional-behavioral responses and altered interactions may therefore increase behavioral and psychological symptoms of dementia (BPSD). We hypothesize that improving caregiver affect through self-care may also reduce BPSD in the care recipient.

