Theoretical Framework. The proposed study is based on the Transactional Model of Stress and Coping. Stressful experiences such as caregiving demand – circumstances that give rise to real or perceived stress – are construed as person-environment transactions. Primary appraisal of demand involves assessment of its significance, which results in perceived burden. Secondary appraisal involves assessment of the resources available to cope with it. These appraisals lead to the coping effort.

Without successful coping, self-care is poor, which decreases health status in caregivers. Our virtual support intervention [ViCCY (“Vicky”) – Virtual Caregiver Coach for You] addresses both appraisal and coping. Because stress does not affect all people equally, the intervention is tailored to individual appraisals and the factors most likely to influence demand and perceived burden. A key strength of the Transactional Model of Stress and Coping is its recognition that both individual and environmental variables respond to coping.

Scientific premise. This study builds on a strong body of evidence that describes stress and poor self-care in FTD caregivers. Health coaching has been shown to decrease perceived stress and improve self-care and health status in Alzheimer’s dementia caregivers, however FTD caregivers are a unique group who are most at-risk for poor self-care, stress and depression. Furthermore, in addition to our primary aims, we will explore the impact of caregiver mood on patient behavioral outcomes. Although a growing body of research illustrates the influence of caregivers on patients and vice versa, (i.e., dyadic processes), we are not aware of intervention studies that have explored the influence of the FTD caregiver mood on behavioral and psychological symptoms (BPSD) in the patient.

CHARACTERISTICS OF THE STUDY POPULATION:

1. Target Population and Accrual:

In the proposed randomized clinical trial, we will enroll adults who are informal caregivers of adults with bvFTD and the bvFTD patients they care for. The study focuses on the caregivers, but we will also enroll bvFTD patients because we will be collecting patient demographic and disease severity (i.e., modified Clinical Dementia Rating Scale) information.

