- Caregiver is providing care at least 8 hours /week
- Able to see, hear, speak and read English
- Not planning to move out of the area soon
- Not participating in another support study

2. If appropriate, RA will continue with the full screening process by assessing the following:

- Reporting poor self-care on screening (Health Self-Care Neglect scale score greater than or equal to 2)
- Telephone Interview for Cognitive Status (TICS) score <25

After screening, the RA will obtain informed consent from caregivers to continue with study procedures. Those who agree to participate will be asked to read and sign the consent form with integrated HIPAA authorization information (i.e., specifics about data elements to be collected and use of the private information). Fully eligible caregivers who provide informed consent will complete the baseline assessment before being randomized to study arm. After all baseline data is collected the caregiver will be randomized to study arm. At that time, participants will be trained in tablet use and how to access the Health Information website. We will seek bvFTD patient consent to review their medical records and to complete the modified Clinical Dementia Rating Scale (mCDR).

Remote enrollment. In the event that written consent cannot be obtained in person due to safety or practical reasons we will telephone caregivers who have expressed a willingness to speak with us about the study or were referred to us by clinical or other research staff. We will explain the study and screen those who are interested in participating. The screening will be done by telephone. Those who are eligible to participate will be pushed an electronic link that begins with the consent form. Staff will talk through the consent in detail. If the caregiver wishes to think about the study but not commit at this time, we will contact him/her at a later date. If the caregiver immediately decides to participate, the consent can be signed electronically. Once signed, the full enrollment survey will be available for completion. Staff will offer to stay connected and support survey completion for those who wish support.

5. Early Withdrawal of Subjects:

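### The exploratory Aim 2 model has no arm term, and the plan names no informant or follow-up visits for FTD-FRS and NPI; if unblinded caregivers supply these scores, changed reporting could pass for patient change

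*Combined protocol and SAP*

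**What the plan says.** The aim is exploratory but causally worded (OBJECTIVES): "Aim 2: Explore the effect of caregiver outcomes on FTD patient outcomes". The contrast is pooled over arms: "FTD patients whose caregivers improve vs. not improve in self-care – regardless of group – will demonstrate H2a" fewer behavioural symptoms on the FTD rating scale (primary) and the NPI (secondary), at 6 months.

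STUDY PROCEDURES, 5. Statistical Analysis gives the Aim 2 model: repeated patient scores with the mean-centred baseline score as covariate, and "Other predictor variables will include time-dependent caregiver variables, assessment time, and the corresponding two-way interaction term (primary effect of interest". The Aim 1 model in the same section does name arm: "Other predictor variables will include group, assessment time, and the interaction of group time (primary effect of interest". The general adjustment clause there covers chance baseline imbalances, and arm is not one of these.

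On measurement:
- METHODS, 1. Study Instruments names the FTD-FRS and NPI without an informant or rater. Baseline is the only time given for patient measures.
- METHODS, 6. Subject Follow-up and STUDY PROCEDURES, 1. Detailed Description list the phone assessments at 3 and 6 months. Neither list includes the FTD-FRS or NPI.
- Subject Recruitment and Screening states what is asked of patients: "We will seek bvFTD patient consent to review their medical records and to complete the modified Clinical Dementia Rating Scale (mCDR".
- METHODS, 3. Method for Assigning Subjects to Groups blinds investigators and the staff who collect assessments, but not caregivers.

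**The concern.** Comparing caregivers who improve with those who do not is not a randomised comparison. If coaching works as H1a expects, arm shifts self-care. If arm also shifts how symptoms are described, leaving it out creates an association between the two with no change in any patient.

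A second route does not involve arm. If one person supplies both the self-care score and the symptom scores at one assessment, that person's state on the day enters both. The BACKGROUND makes this plausible without showing it: "Caregivers often misinterpret patient behavioral symptoms such as apathy or disinhibition as a sign of volitional opposition and poor cooperation", and the intervention "addresses both appraisal and coping". The same section also notes influence from patient to caregiver, so an easier patient who leaves more time for self-care would produce the same association.

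At stake is the reading of a positive Aim 2 as evidence that caregiver self-care improves patient behaviour.

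**Working it through.** **No plan figure to reproduce.** The only power statement (over 90% with 15 caregivers per arm) concerns the Self-Care Inventory under Aim 1. Nothing is stated for Aim 2.

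**Inputs.** From the documents: 30 dyads, 1:1 allocation, 5% level (two-sided assumed). Assumed, because the documents give nothing: the share c of variance in both reports that is one shared reporting state, and the arm shifts in self-care and in reporting. The true patient effect is set to zero throughout.

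**Step 1: association of same-visit change scores.** A shared share c gives a correlation of size c. The Fisher approximation for the rejection rate, with δ = atanh(r)·√(n−3) and √27 = 5.196, is 1 − Φ(1.96 − δ) + Φ(−1.96 − δ).
- r = 0.1: δ = 0.521, rate 8.2%
- r = 0.2: δ = 1.053, rate 18.4%
- r = 0.3: δ = 1.608, rate 36.3%

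Simulation of the same set-up (20,000 runs) gave 8.1%, 18.6% and 36.7%.

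**Step 2: arm effects.** Assume arm moves self-care by 0.8 SD and symptom reporting by 0.5 SD. With equal arms this adds a covariance of 0.25 × 0.8 × 0.5 = 0.10. The variances become 1 + 0.25 × 0.64 = 1.16 and 1 + 0.25 × 0.25 = 1.0625, and √(1.16 × 1.0625) = 1.110.
- Arm effects only: r = 0.10/1.110 = 0.090, rate 7.6% (simulated 7.5% to 7.8%). With an arm term the rate is about 5%.
- Arm effects plus c = 0.2: r = 0.30/1.110 = 0.270, rate 30% (simulated 31%).
- The same with arm adjusted: r = 0.2, one degree of freedom fewer (√26 = 5.099), δ = 1.034, rate 17.9% (simulated 18%).
- The same with arm adjusted and lagged self-care, if the reporting state has an assumed autocorrelation of 0.4: r = 0.2 × 0.4 = 0.08, δ = 0.409, rate 6.9% (simulated 6.9%).

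**Step 3: 6-month score regressed on its baseline and self-care** (20,000 runs; g is an arm shift in SD applied to both reports):

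| c | g | no arm term | arm term |
|---|---|---|---|
| 0 | 0 | 5.2% | 5.2% |
| 0 | 0.5 | 6.7% | 5.1% |
| 0 | 1.0 | 24.7% | 5.1% |
| 0.2 | 0 | 24.4% | 23.6% |
| 0.2 | 0.5 | 34.0% | 23.3% |
| 0.4 | 0 | 71.8% | 70.1% |

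The arm term removes what arm contributes and leaves the within-arm part almost untouched.

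**Step 4: the term the plan calls primary.** The interaction asks whether the self-care slope differs between visits. A bias that is equal at both visits cancels in that difference. A two-visit random-intercept model (4,000 runs, no arm term; the planned random slope was not fitted) shows this:
- Constant c = 0.2: 6-month slope 35%, interaction 5.5%.
- c rising from 0 at 3 months to 0.3 at 6 months: 6-month slope 54%, interaction 27%.

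**The case against.** A reader might infer that the same unblinded caregiver certainly reports patient symptoms at the same visit. The documents do not support that as fact. They name no informant, assessment staff are blinded, charts are reviewed, and neither scale is scheduled after baseline. The inference is reasonable, since patients are asked only for record review and the mCDR, follow-up is by phone, and no independent rater appears. It remains an inference. Blinding the staff who record answers does not blind the person who gives them.

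The rates in Steps 1 to 3 might be read as error rates of the planned Aim 2 test. They are not: they describe a change-score or 6-month association. This limits the claim but does not dispose of it, because H2a is posed at 6 months and the 6-month slope is distorted either way. Changing bias is also conceivable when coaching is front-loaded and tapers.

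The missing arm term might be taken as the main cause. At the assumed effects it accounts for little by itself (about 7.6% against 5%), and adding it does not cure a shared-reporter bias.

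The BACKGROUND passages can be over-read too. Misinterpretation there concerns the cause of behaviour rather than its presence or severity, and appraisal concerns caregiving demand and resources. They make altered reporting plausible and no more.

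Finally, pooling is declared and the aim is exploratory. Declaring that the contrast ignores group is compatible with adjusting for arm. However, adjustment does restrict the estimate to within-arm variation in self-care, which is a real trade-off. The exploratory label lowers the severity.

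**Conclusion.** The concern holds in a limited form. It is on the page that the Aim 2 model lists no arm term, that the contrast is non-randomised and pooled but worded as an effect, that caregivers are unblinded, and that the informant and follow-up visits for the FTD-FRS and NPI are not stated. If the caregiver supplies these scores at the same assessment, a 6-month association cannot distinguish patient change from changed reporting, and its direction stays open.

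The size is illustrative only: roughly 8% to 37% false positives for change scores with a shared share of 0.1 to 0.3, and about 10% to 72% for the 6-month regression with a share of 0.1 to 0.4. All shares and shifts are assumptions. The planned interaction with time keeps close to its nominal level under constant shared reporting. If the informant proves to be independent, the shared-reporter part falls away, but the points on arm, direction and wording remain. This is a lower-severity point.

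**What to change.** 1. Add randomised arm and arm x time to the Aim 2 model.
2. Beside it, as a sensitivity analysis, report a lagged model: Self-Care Inventory change from baseline to 3 months predicting the 6-month patient score, adjusted for its baseline.
3. State who supplies the FTD-FRS and NPI, and list both scales at the 3- and 6-month visits. Word H2a and its conclusion as an association, with symptoms called caregiver-reported if the caregiver is the informant.

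The cost is SAP wording and one more model. The 6-month patient scores it uses are already needed for H2a. The arm terms take one or two degrees of freedom from 30 dyads, the lagged model ignores self-care change after month 3, and the claim becomes more modest. Within-arm shared-reporter bias remains after step 1. Step 2 reduces it only as far as the reporting state fades between visits, which is why the wording in step 3 is needed.
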